## 9.0 STUDY AGENT (STUDY DRUG, DEVICE, BIOLOGIC, VACCINE, ETC.) AND/OR PROCEDURAL INTERVENTION

### 9.1 Study Procedural Intervention(s) Description

- For devices: The labeling will contain the statement "CAUTION - Investigational Device. Limited by Federal (or United States) Law to Investigational Use."

#### HD-tDCS Stimulation protocol

There will be two groups/arms in this trial,

- A group that will receive HD-tDCS treatments and cognitive training (CT) (n=10),
- A group that will receive sham HD-tDCS treatments and cognitive training (n=10).

HD-tDCS/sham HD-tDCS sessions combined with CT will be administered in monthly blocks of 5 consecutive daily sessions for a total of 15 treatments or 3 monthly blocks. For that, treatments will be administered at the MCW facilities or the UW Hospital. Study personnel may also visit subjects at their homes to administer the intervention if the subjects prefer. The safety and feasibility of home delivery of this intervention is supported by the existing literature (Im et al., 2019). Both HD-tDCS and sham-HD-tDCS treatments will be administered during a cognitive training session. The HD-tDCS procedure is described in detail below. We will sequentially stimulate or sham stimulate four networks, left and right frontal and left and right temporoparietal with 1.5mA. Each network will be stimulated/sham-stimulated for 20 min for a total of an 80 min stimulation session. On Mondays prior to CT and Fridays after CT, subjects will be assessed on competency and ability to perform the CT. The CT blocks will start after 5 min of stimulation of each network and will last 15 min/network (total 60min/session).

**Figure 5:** HD-tDCS devices and HD-Cap (bottom right)

#### Detailed description of the HD-tDCS procedure

When conducting HD-tDCS, specially designed insets, electrodes, stimulation protocols, and conductive gels will be used. Appropriate instrumentation, electrode design, and protocols are considered important for HD-tDCS safety and comfort. A flexible cap will be placed on each participant's head.

The electrode casings or holders will be secured in the cap. The skin prepping guidelines as listed in Villamar et al. (2013a) will be followed: separating the hair inside the electrode casings until the scalp is exposed, removing hair products and dirt on the scalp using alcohol swabs and then filling the electrode casings with 3 mL of Signa Gel (Parker Laboratories, NJ) or HD-GEL™ (Soterix Medical) with more applied if needed. The electrodes will be placed on a platform inside the casings so that they are completely immersed in the gel. More gel will be applied to cover the electrodes if needed, and then they will be held in place with the casing caps. Impedance values will be examined for all the electrodes and will all be verified to be <2 quality units.

The electrodes will be connected to a Soterix Medical 1x1 low-intensity DC stimulator (UW-Madison, Figure 5, top panel) or a Soterix MxN-9 High-Definition stimulator (MCW, Figure 5, bottom panel). Software packages such as SimNIBS 2.1 (Saturnino et al., 2018 bioRxiv) and those available through Soterix Medical (HD-Targets/HD-Explore) may be employed for current flow and electric field modeling for HD-tDCS. At MCW, we may use patient's structural MRI, (baseline or the one obtained for routine clinical standard of care), for modeling and/or for navigating to the HD-tDCS electrode positions from the brain surface on to the patient's scalp, using Transcranial Magnetic Stimulation (TMS).

Participants will be randomized to receive real or sham HD-tDCS. For real HD-tDCS, the device will be ramped up to 1.5 mA and maintained at this current for 20 minutes. For sham HD-tDCS, the device will be ramped up to 1.5 mA, but after 30 seconds, will be ramped back down to 0 mA and stay off for the remainder of the 20 minutes for a total of an 80 minutes of stimulation session. The MxN-9 device allows for pre-programming by an unblinded member of the study team that will not be present during the

stimulation procedures. The device operator and the study subject will therefore remain blinded to the stimulation condition.

In the case of the Soterix Medical 1X1 low-intensity stimulator, an unblinded study member will set-up the device and leave the room after covering or hiding the sham button or switch (e.g. using black tape). This will guarantee the blinding of both, the study participant and the device operator.

Each cognitive training session will last a total of 60 minutes; This will be achieved by starting cognitive training 5 minutes after the initiation of tDCS (i.e. a total of 15 minutes of cognitive training per network).

### **Method of electrode positioning for HD-tDCS**

There are two approaches that we will explore for HD-tDCS electrode positioning: 1) electrode positioning will be the same for all patients and will be based on the International EEG 10-20 system and 2) electrode positioning may be different across patients, but guaranteeing the same cortical targets across all patients, as determined using the software packages mentioned in the earlier section (Figure 3). For #1, according to the diagram presented in figure 6 of the protocol, the positions FP1, FP2, CP3, CP4 will be the anodes for each of the four networks and 10 positions P1, PZ, P2, FT9, FT10, FCZ, POZ, PO9, PO10 will be used as cathodes. The assignment of the electrodes to the 4 different networks is outlined in the diagram in figure 3.

The placement of electrodes is based on landmarks on the skull, namely the nasion (Nz), the inion (Iz), and the left and right pre-auricular points (LPA or T9 and RPA or T10). The first step is to form the line from Nz to Iz, over the vertex (Figure 6).

To determine the location of the vertex, the contour from LPA (T9) to RPA (T10) is also passed over the vertex. These two contours should intersect at 50% of their lengths and the point thus obtained is the exact vertex. Along the sagittal Nz-Iz scalp contour over the vertex, the positions Fpz, AFz, Fz, **FCz**, Cz, CPz, Pz, POz and Oz are marked at 10% distances along this antero-posterior contour. With position Cz at 50% along this contour, corresponding to the vertex, the position of Oz is at a distance of 90% from Nz and 10% from Iz.

Along the coronal LPA-RPA scalp contour over the vertex, the positions at 10% above the LPA and the RPA are marked. These positions are necessary to determine the horizontal contours over the left and right temporal lobe.

A horizontal circumferential contour is determined over the left temporal lobe from Fpz to Oz, through the location which was marked at 10% above LPA. Along this contour, the positions **Fp1**, AF7, F7, FT7, T7, TP7, P7, PO7 and O1 are determined at 10% distances. The circumferential contour over the right temporal lobe is determined in the same fashion

**Figure 6:** Method of electrode placement according to the 10/10 system.

from Fpz to Oz over the location 10% above RPA, and the positions **Fp2**, AF8, F8, FT8, T8, TP8, P8, PO8 and O2 are marked at 10% distances.

[figure not shown]
A horizontal circumferential contour is determined over the left side of the head between T9 (LPA) and Nasion (Nz). Along this contour, the position **FT9** is determined at 20% distances. The circumferential contour over the right side is determined in the same fashion, this leads to placement of electrode **FT10**. A horizontal circumferential contour is determined over the left side of the head between T9 (LPA) and Inion (IZ). Along this contour, the position **PO9** is determined at 40% distance from the IZ. The circumferential contour over the right side is determined in the same fashion, this leads to placement of electrode **PO10**.

The positions for anodal electrodes **Fp1**, **Fp2**, **CP3** and **CP4** and the cathodal electrodes **P1**, **Pz**, **P2**, **PO9**, **PO10**, **FT9**, **FCZ**, **POZ** are marked with a waterproof permanent marker using **red color for the anodes and black color for the cathodes**.

The markings will be maintained and refreshed from session to session to minimize need for new measurements. Whenever the markings fade, new measurements using the same landmarks will be performed in a stereotypic fashion.

The devices used are made by Soterix Medical and were used in the previous adult studies without incident. They are marked as Investigational Use Only. The first set of devices are 1) a low-current low-voltage tDCS sources; 2) a tDCS splitter box.

The low-voltage low-current source generates a low intensity current for the duration of the stimulation. It is powered by 9V batteries and limited to 2 mA maximum. In this study we will use intensities of 1.5 mA or below as a safety factor. The splitter does not actually generate any stimulation. It can be thought of as a passive splitter box. For #2, we will use the MxN-9 Soterix stimulator; note that a splitter box is not needed with this device. Modelling will be performed on every patient taking into account the size and shape of the head and the skull thickness. If the anticipated peak electric field at 1.5 mA exceeds 0.654 V/m in the brain tissue, the current will be

reduced from 1.5 mA to a lower calculated value, so that the maximal field intensity of 0.654 V/m is not exceeded. Peak electric field of 0.654 V/m is observed in adults who receive tDCS with 2mA total current (Figure 2; Borckardt et al., 2011).

The output cable of the splitter box or the MxN-9 device connects to the STENs electrodes, which are immersed in the SIGNA gel or HD-GEL that is held in place by the plastic insets (or electrode casing caps), which are mounted on to the cap.

Dermal abrasion is not typically required for a good contact, however, gentle moving of hair and working of gel into skin might be used – Just as done for EEG.

### Cognitive training

We will use the Posit Science's brain plasticity-based BrainHQ exercises platform (<https://www.brainhq.com>). The BrainHQ platform consists of more than two dozen exercises grouped into six broad categories: Attention, Memory, Brain Speed, Intelligence, People Skills, and Navigation. These general categories clearly overlap and the assignment of any given game to one single specific category is a matter of predilection for a cognitive domain, and not a matter

of absolute specificity (e.g., a game under the 'Memory' category will inevitably recruit 'Attention' and 'Brain speed' mechanisms, both cognitive functions necessary for adequate memory formation).

All participants will receive active Computerized CT which will be administered for 60 min during HD-tDCS or sham HD-tDCS sessions.

Participants will engage in exercises of increasing complexity designed to train attention, memory, processing speed, people skills and navigation. To maximize the synergistic effect of HD-tDCS and CT on the same brain region, we plan to couple the electric stimulation of a network with a game that has a preferential effect on that same network (e.g. left temporoparietal stimulation with a verbal memory task, and right temporoparietal stimulation with a non-verbal memory task).

For this purpose, we will select 12 games (out of an approximate total of 29) and assign each one of them to one of the four possible networks that will be stimulated (see table 3).

**Table 3:** Training Schedule

Brain Network	Monday	Tuesday	Wednesday	Thursday	Friday
Left frontal	1) Divided attention 2) Mixed signals 3) Mind bender				
Left temporo-parietal	1) memory grid 2) Face-facts 3) In the know				
Right frontal	1) Eye for detail 2) Target Tracker 3) Double decision	1) Eye for detail 2) Target Tracker 3) Double decision	1) Eye for detail 2) Target Tracker 3) Double decision	1) Eye for detail 2) Target Tracker 3) Double decision	1) Eye for detail 2) Target Tracker 3) Double decision
Right temporo-parietal	1) Hear, Hear 2) Right turn 3) Recognition				

Choosing 12 games out of a larger pool of 29 will allow us to narrowly select those games better suited for the stimulation of the 4 proposed brain networks for every block (3 games/network). The selection of 12 games will also facilitate scheduling (3 games/network/day).

The combined HD-tDCS/sham HD-tDCS and CT sessions will be performed monthly on 5 consecutive days for 3 months. A study coordinator will visit each participant at their homes or meet them in the hospital for a session. The laptop with the appropriate software will be provided by the investigator team.

The weekly training schedule is outlined in table 3. A 'Personalized Trainer' option will present an automated sequence of the chosen exercises. Participants will have identical sessions initially, but

later they will be given different sessions based on their individual performance history (3 games/network will always remain a constraint). The active training blocks will each last 15 min.

### **Procedures for Training of Clinicians on Procedural Intervention**

The study interventions will be administered by a research specialist or the study coordinators who will be trained by Drs [name], [name], [name], and [name] in administering HD-tDCS and cognitive training.

## **9.2 Method for Assigning to Treatment Groups**

Randomization to the two arms will be the responsibility of an unblinded member of the study team.

## **9.3 Unblinding Procedures**

Unblinding will be done in emergent circumstances where the identity of the treatment needs to be known. All efforts will be made to maintain blinding except in the case of urgent medical necessity.

## **9.4 Study Intervention Compliance**

Threshold adherence/compliance is achieved when the enrolled participant completes all HD-tDCS/sham HD-tDCS + CT sessions and undergoes cognitive testing at 0, 3 and 6 mo. This degree of participation will allow calculation of the primary outcome, i.e. treatment completion rates.

## **9.5 Concomitant Therapy**

### **Permitted Concomitant Therapy**

Subjects will continue all medications and other prescribed treatments during participation in this study. No life style changes are necessary.

### **Prohibited Concomitant Therapy**

None

## 10.0 STUDY VISITS AND PROCEDURES

### 10.1 Study Calendar

The procedures performed at each study visit are listed in the table below.

Visit	Baseline	Treatment Period			Month 3	Month 6	Early Withdrawal
	1	2-6	7-11	12-16	17	18	
Visit Window	-6 months		±4 weeks	±4 weeks	Up to 6 weeks post Visit 16	3 months post Visit 16 ± 8 weeks	
Timeframe		Week 1 (Month 1)	Week 2 (Month 2)	Week 3 (Month 3)			
Informed Consent	X						
Review Eligibility Criteria	X						
Demographics	X						
Review Concomitant Medications	X				X		X
Obtain Medical History	X						
Physical Exam	X				X		X
Vital Signs 	X				X		X
Randomization	X						
Study Partner Questionnaires	X				X	X	
Cognitive Battery	X				X	X	
MRI	X				X 		
TMS Neuronavigation (for stimulation planning) MCW only	X						
Device Administration		X	X	X			
Adverse Events Review/Assessment		X	X	X	X	X	X

1 Vitals include: pulse rate, body temperature, blood pressure, respiration rate, height, and weight

2 MRI will aim to be completed within 6 week window, but can be completed up to 12 months after Visit 16 if scheduling problems arise

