## **Protocol Version History**

Protocol Version	Version Date	Summary of Revisions Made	Rationale
1.0	12/13/2019	Initial version	
2.0	10/30/2020	Revised Cognitive Battery, UW ADRC Recruitment letter added, Study Partner Questionnaires added to study visits, Study Partner Questionnaires description added, Study Partner compensation added, Quality of Life Questionnaires removed from study visits and secondary endpoints, exclusion criteria updated to reflect need for study partner, Study Visit Calendar updated to reflect changes	
3.0	01/13/2021	Moved follow-up MRI to Month 3, expanded visit windows, 3.1 Objectives changed, Table 3.2 updated, 6.0 and 12.1 secondary endpoints updated	Follow-up MRI moved to Month 3 as we expect long-term effects of this multifield extended approach to tDCS, expanded visit windows to account for potential COVID-19 disruptions and increased subject retention

4.0	04/15/2021	
 
1. Increased subject recruitment to 20 subjects and study partners,
 
2. removed handedness from inclusion/exclusion criteria,
 
3. increased Day 1 visit window to 6 months,
 
4. removed Day 1 AE evaluation,
 
5. added potential for subject interchangeability between sites
 
6. formatting modifications
 
	
 
1. Increased recruitment number to account for screen fails and withdrawals
 
2. Revised inclusion/exclusion criteria to improve recruitment
 
3. Day 1 visit window extended to improve subject retention
 
4. Day 1 AE evaluation removed as visit occurs prior to tDCS/sham administration
 
5. Interchangeability between sites added to improve subject retention and dataset completion
 
6. Formatting modifications to improve readability
 

5.0	10/15/2021	
 
1. Section 8.5 – modified to include reimbursement for hotel or other form of lodging. MCW subjects may be eligible to stay at Kathy's House
 
	
 
1. We are offering lodging assistance to improve enrollment and retention
 

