	
 
• Consent rate
 
• ADCS PACC score at 3 and 6 months
 
• Neurite density (intracellular volume fraction) at 3 months
 
• Diffusivity indices: Fractional anisotropy (FA), Mean (MD), Axial (AD), Radial (RD)
 
• Diffusivity at 3 months
 
• Morphometric indices: Cortical thickness, Surface Area, Volume, gyration index at 3 months.
 
• ASL perfusion indices: blood flow, blood volume, mean transit time, time to peak, at 3 months
 

Study Design	The study design is a double-blinded, randomized pilot clinical trial of HD-tDCS/sham HD-tDCS combined with CT, administered to subjects with amnestic MCI (aMCI) in blocks of 5 daily treatments for a total of 15 sessions. There will be one treatment block/month for a total of 3 months. 20 participants with aMCI will be enrolled. There will be 2 treatment groups/arms with 10 subjects per group/arm. We anticipate a dropout rate of appr. 10% and aim to complete procedures in 20 subjects.
Study Intervention	High definition transcranial direct current stimulation (HD-tDCS) Sham HD-tDCS Computerized Cognitive training (CCT) Sham CT
Total Number of Subjects	20
Study Population	Male and females aged 50 to 90 years with established diagnosis of MCI amnestic type. Total of 20 subjects
Statistical Methodology	Given the pilot nature of this study, two feasibility outcomes will be included: Consent rate and treatment completion rate. 20 patients are enough to calculate a 90% exact binomial confidence interval of (.75, 1) if all 20 are observed to complete treatment. Thus, this sample size is large enough to potentially exclude completion rates of 3/4 or lower. The pilot data from this study will provide initial estimates of the variability and the effect sizes. This information will then be used for the formal calculations of power and sample size necessary to conduct a future phase II trial.
Estimated Subject Duration	The duration of the study for each subject is approximately 6 months.
Estimated Enrollment Period & Study Duration	Study enrollment and follow-up will occur over 9 months with the total expected duration of the trial to be 12 months.

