### **Visit 17 (Month 3)**

At this visit, the following procedures and tests will occur:

- Neuro and physical exam
- Vitals signs
- Cognitive battery
- Study Partner Questionnaires
- Structural MRI (will aim to be completed within 6 week window, but can be completed up to 12 months after Visit 16 if scheduling problems arise)

This visit will be approximately 6 hours and will likely be completed in 1-2 days but can be completed over multiple days.

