# 12.0 STUDY ANALYSIS

## 12.1 Statistical Hypotheses

- **Primary Efficacy Endpoint(s):**

Treatment completion rates.

- **Secondary Efficacy Endpoint(s):**

- Consent rate.
- ADCS-PACC score at 3 and 6 months
- Neurite density (intracellular volume fraction) at 3 months
- Diffusivity indices: Fractional anisotropy (FA), Mean(MD), Axial(AD), Radial(RD) Diffusivity at 3 months
- Morphometric indices: Cortical thickness, Surface Area, Volume, gyration index at 3 months
- ASL perfusion indices: blood flow, blood volume, mean transit time, time to peak, at 3 months

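### A scan labelled '3-month' may by exception be taken up to 12 months after Visit 16, and the Month 3 and Month 6 cognitive windows overlap at their edges with no minimum gap

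*Combined protocol and SAP*

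**What the plan says.** **Imaging.** The Synopsis (Section 3.1), Section 6.0 and Section 12.1 attach the imaging outcomes to 3 months, for example "Neurite density (intracellular volume fraction) at 3 months". The Study Calendar (Section 10.1) places the follow-up MRI in the Month 3 column, Visit 17, whose window is "Up to 6 weeks post Visit 16". Footnote 2 treats the 6 weeks as an aim for the MRI and adds that it "can be completed up to 12 months after Visit 16 if scheduling problems arise". The Visit 17 text in Section 10.2 repeats this: "Structural MRI (will aim to be completed within 6 week window, but can be completed up to 12 months after Visit 16".

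**Cognition.** ADCS-PACC is an endpoint at 3 and 6 months, and the battery is given at Visits 17 and 18. The Visit 18 window is "3 months post Visit 16 ± 8 weeks". No minimum interval between the two visits is stated in the calendar, Section 10.2 or Section 12. Section 8.6 has the site try to rebook a missed visit within 6 weeks.

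**Durations.** The Synopsis states: "The duration of the study for each subject is approximately 6 months". It gives the "total expected duration of the trial to be 12 months".

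**Reason for wide windows.** The version history gives this rationale for version 3.0: "expanded visit windows to account for potential COVID-19 disruptions and increased subject retention".

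**Analysis.** Section 12 contains no rule for a scan outside the 6 weeks or for two cognitive tests held close together. Most of Sections 12.3 and 12.4 describes a future phase II trial.

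**The concern.** The label and the permitted timing disagree. A scan taken close to a year after the last scheduled session would, on the text as written, be reported as a 3-month result. Section 12.2 uses the pilot for initial estimates of variability and effect size, and it places the phase II MRI at 12 months. A reader of the pilot therefore needs to know which interval its imaging estimates describe. Mixed timing under one label adds variance and leaves that interval unclear. Late scans also have more opportunity to differ in site (Section 10.1, Screening and Enrollment) or in sequence, which the MRI text allows to change during the study.

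For cognition, Section 5.4 sets out to test at 6 months whether effects last. If Visit 18 may fall 4-5 weeks after treatment, inside the Month 3 window, the Month 6 label no longer guarantees a later time point.

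**Working it through.** The plan states no figure to reproduce, so this is interval arithmetic on its windows, with Visit 16 as week 0.

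**Inputs.** From Section 10.1 (Study Calendar): Visit 17 at weeks 0-6; Visit 18 at 3 months ± 8 weeks; MRI aim 6 weeks, limit 12 months; baseline window 6 months; blocks 2 and 3 each ± 4 weeks. The documents do not convert months to weeks. I take 1 month = 365.25/12/7 = 4.348 weeks, and 3 months = 12 weeks as the alternative.

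**1. MRI limit.**
- 12 × 4.348 = 52.18 weeks.
- Past the aim: 52.18 − 6 = 46.18 weeks, or 46.18/4.348 = 10.6 months.

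**2. Visit 18 window.**
- 3 × 4.348 = 13.04, and 13.04 ± 8 gives weeks 5.04 to 21.04.
- 12-week reading: 12 ± 8 gives weeks 4 to 20.
- The MRI limit is 52.18 − 21.04 = 31.1 weeks after the latest in-window Visit 18. A scan between weeks 6 and 21 uses the exception but is not later than every in-window Month 6 visit.

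**3. Overlap of Visits 17 and 18.**
- 6 − 5.04 = 0.96 week, which is 0.96/16 = 6% of the 16-week Visit 18 window.
- 12-week reading: 6 − 4 = 2 weeks, 2/16 = 12.5%.
- Actual calendar spans of 89-92 days give 1.29 to 0.86 weeks.
- The permitted gap between the two visits runs from about 0 to 21 weeks.
- If a Visit 17 missed at week 6 is rescheduled 6 weeks later (my reading of Section 8.6), it falls at week 12. The overlap is then 12 − 5.04 = 7.0 weeks, or 12 − 4 = 8 on the 12-week reading.

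**4. Stated durations.** A scan at the full limit is by construction more than 12 months after that subject's first session, so it exceeds the expected trial length. An earlier scan under the exception may or may not, depending on when the subject started.

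**5. Time from first session or baseline (assumption-dependent).** With blocks one month apart, Visit 16 falls (60.9 + 4)/7 = 9.27 weeks after the first session. The calendar does not say what the ± 4 weeks are measured from. Make-up sessions are ignored.

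| Block-window assumption | Visit 16, week | Latest scan after first session | Longest baseline-to-scan, in window | Longest, with exception |
|---|---|---|---|---|
| On schedule | 9.27 | 9.27 + 52.18 = 61.4 wk (14.1 mo) | – | – |
| One +4 weeks | 13.27 | 65.4 wk (15.1 mo) | 26.09 + 13.27 + 6 = 45.4 wk | 26.09 + 13.27 + 52.18 = 91.5 wk |
| +4 weeks compounding | 17.27 | 69.4 wk (16.0 mo) | 49.4 wk | 95.5 wk |

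The last two columns stack separate extremes and describe what is permitted, not what is likely.

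**6. Illustrative effect on imaging variance.** Assume a fraction p of scans is displaced by d SD. Variance rises by the factor 1 + p(1 − p)d². The documents give neither p nor d.
- p = 0.1, d = 0.25: 1 + 0.09 × 0.0625 = 1.006.
- p = 0.2, d = 1: 1 + 0.16 × 1 = 1.16.
- For comparison, the 95% interval for a variance pooled over two arms of 10 (18 df) is 18/31.53 = 0.57 to 18/8.23 = 2.19 times the estimate.

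**The case against.** The best case for leaving the text alone is that the late scan is a stated exception for scheduling problems. Keeping a late scan is better than losing it in a 20-subject pilot, and the windows were widened for sound reasons. The durations in the Synopsis are approximate. The cognitive overlap lies at the window edges. The battery alternates three test versions to limit learning effects. Section 12 is written mainly for phase II, so its silence on pilot timing is part of a wider gap. All of this stands, and it sets the grade. It does not remove the mismatch: the alternating versions do not separate two time points, and a retention allowance does not make a late scan a 3-month scan.

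Some stronger readings are tempting, but the documents do not support them:
- *Every scan under the exception is later than Month 6 and outside the trial.* This holds only for part of the range, after about week 21 and, for trial length, depending on the subject's start.
- *The Month 3 versus Month 6 comparison is compromised.* The endpoint is the score at each time. The plan defines no contrast between them, and testing whether effects last at 6 months can be read as the effect at that visit.
- *Late scans bias the arm comparison.* Nothing in the documents makes lateness depend on arm.
- *The primary endpoint or phase II sample size is affected by scan timing.* MRI is not part of threshold adherence (Section 9.4), and the phase II calculation rests on ADCS-PACC (Section 12.2).

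**Conclusion.** The point holds and is minor. The plan allows a scan labelled 3-month to be taken up to 46 weeks past its 6-week aim, and up to 31 weeks after the last in-window Month 6 visit. That limit does not fit the stated participation and can exceed the expected trial duration. The Visit 17 and Visit 18 windows overlap by about 1-2 weeks, the range depending on how 3 months is converted to weeks, and no minimum gap is set. These results need only the calendar. Figures from first session or baseline also depend on how the block windows are anchored. The finding that no timing rule exists is a reading of silence. On the illustrative assumptions the imaging variance rises by 0.6-16%, which is small beside the sampling error of a trial this size. The case for acting is that the estimates would be interpretable at little cost, not that they would otherwise be seriously wrong.

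**What to change.** 1. Keep the late-scan allowance. Pre-specify that the 3-month imaging estimate uses scans within 6 weeks of Visit 16, and show the all-scan estimate beside it.
2. List each scan's time since baseline and since Visit 16, with its site and sequence version.
3. Reconcile the 12-month allowance with the 3-month label and with the stated participation and trial durations. State what the block windows are measured from.
4. Reconcile the Visit 17 and Visit 18 windows so that they do not overlap. Set the minimum gap between the actual visits, so that it also covers a Visit 17 rescheduled under Section 8.6. Moving only the nominal window edge would not.
5. Report ADCS-PACC by visit number with actual time since Visit 16, and put visits held close together in a sensitivity listing. Say that this listing does not change who counts as a completer under Section 9.4.

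The cost is wording in the calendar and Section 12, plus listings; no scan or score is discarded. The in-window imaging set will be smaller and is selected after randomisation, so it should stand beside the all-scan result and not replace it. Scheduling of Visit 18 becomes slightly less flexible.
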